8.2 Analysis of other efficacy variables

8.2.1 Subjects with partial onset seizures

All of the following variables are summarized for the Efficacy Population for POS.

8.2.1.1 Specified Month seizure freedom

The numbers and percentages of subjects who are seizure free for all seizure types for any continuous 6-month interval, 12-month interval, 18-month interval, and so forth will be summarized overall for the period of time that subjects are being treated with BRV and by Exposure Duration Cohort. The overall summary will present the number and percentage of subjects who reported no seizures for the specified duration of seizure freedom and the seizure diary was completed for at least 90% of days within the seizure-free interval. Subjects whose duration of BRV treatment was less than the specified duration of seizure freedom will be considered failures for seizure-freedom. Summaries by exposure duration cohort will present the number and percentage of subjects who reported no seizures for the specified duration of seizure freedom at any time during the cohort interval (eg, through the end of Month 6 for the 6-month cohort) and the seizure diary was completed for at least 90% of days within the seizure-free interval. Percentages are relative to the number of subjects within each Exposure Duration Cohort.

A subject is seizure free for a 6-month interval if the subject did not report any seizures in the 6-month interval and the seizure diary was completed for at least 90% of days within the seizure-free interval. The percentage of days for which seizure diary was completed within a given 6-month interval will be calculated as follows based on a 30-day month:

$$\% \text{ of days diary was done} = 100 \times \left[\frac{180 - \text{number of days diary was not done in the interval}}{180} \right]$$

A similar calculation applies for 12-month seizure freedom based on 360 days, 18-month seizure freedom based on 540 days, and so forth.

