4.2.2 Other efficacy variables

For subjects with focal-onset epilepsy:

- Percentage of subjects continuously seizure-free for all seizure types (I+II+III) for at least 6 months and at least 12 months during the Evaluation Period

For subjects with generalized epilepsy:

- Generalized (type II) seizure days per 28 days during the Evaluation Period
- Percent reduction in generalized (type II) seizure days per 28 days from Baseline of the previous study to the Evaluation Period

- Responder rate for generalized (type II) seizure days over the Evaluation Period. A responder is defined as a subject with a $\geq 50\%$ reduction in seizure days from the Baseline Period of the previous study.
- Percentage of subjects continuously seizure free for all seizure types (I+II+III) for at least 6 months and at least 12 months during the Evaluation Period

The following will be evaluated separately for subjects with focal-onset epilepsy and subjects with generalized epilepsy:

- Change in QOLIE-31-P scores from Baseline of the previous study to each assessment for the first 2 years and to the last Evaluation Period assessment during the first 2 years

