5.3 Visit schedule

Visits to the clinical site will be scheduled as follows:

- First year:
 - First 3 months: 1 visit every month: Minimal Evaluation Visit (MEV) alternating with the Full Evaluation Visit (FEV)
 - Next 9 months: 1 visit every 3 months: FEV alternating with MEV
- Second and subsequent years:
 - 1 visit every 3 months: MEV alternating with FEV/Yearly Evaluation Visit (YEV)
 - The YEV will be performed every 12 months

A full visit schedule is presented in the following table.

This document cannot be used to support any marketing authorization application and any extensions or variations thereof.

REDACTED COPY

Table 5–2: Visit schedule

First year follow-up		
Month	Visit	Type of visit
M0	V1	EV
M1	V2	MEV
M2	V3	FEV
M3	V4	MEV ^b
M4	-	-
M5	-	-
M6	V5	FEV
M7	-	-
M8	-	-
M9	V6	MEV ^b
M10	-	-
M11	-	-
Second year follow-up^a		
Month	Visit	Type of visit
M12	V7	YEV
M15	V8	MEV
M18	V9	FEV
M21	V10	MEV

EV=Entry Visit; FEV=Full Evaluation Visit; M=month; MEV=Minimal Evaluation Visit; V=Visit; YEV=Yearly Evaluation Visit

Note: “-“ denotes that no visit is scheduled in that month.

^a Subsequent years will follow the same visit schedule.

^b Liver function tests will be performed in addition to the assessments described in Section 8.3

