9 ASSESSMENT OF EFFICACY

Efficacy variables will be assessed using the seizure count information recorded on the DRC.

At each visit, the subject will receive a DRC, to be filled in on days on which a seizure occurs, and to be returned at the next visit. No DRC will be dispensed at the UV or the FV.

The date and the number (where possible) of epileptic seizures will be recorded on the DRC, as well as the type of seizure (according to individual description of seizures), occurrence of clusters, intake of concomitant AEDs, undesirable events with start and end dates, healthcare provider consultations not foreseen per protocol, and changes in concomitant medication, if applicable.

The written information will be discussed with the subject at each visit in order to ensure completeness and accuracy. As a result of the discussion, the Investigator will assess the seizures according to the ILAE codes and record the seizure types and frequency on the CRF; he/she will also confirm the presence of AEs (if applicable). The concomitant medication changes, healthcare provider consultations not foreseen per protocol, and AEs will be reported by the Investigator on the specific pages of the CRF.

The DRC will be considered as source documentation. The subject should be educated to complete the DRC on all days with seizures (eg, when taking evening tablets). Substantial noncompliance with diary completion (seizures recording) may result in subject discontinuation from the study at any time by the Investigator or the Sponsor.

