3.2.5 Monthly time intervals

A month is defined as 30 days and time intervals based on monthly durations are defined as a multiple of 30 days (eg, 12 months is defined as 360 days). The following definitions of 3-month and 6-month intervals are based on 30-day months where the date of first dose of BRV is Day 1:

Interval	Duration Definition
Months 1-3	Days 1-90
Months 4-6	Days 91-180
Months 7-9	Days 181-270
Months 10-12	Days 271-360
Months 1-6	Days 1-180
Months 7-12	Days 181-360
Months 13-18	Days 361-540
Months 19-24	Days 541-720

Subsequent 3- and 6-month intervals are defined in a similar manner.

Six-month intervals are defined for the evaluation of direct and indirect cost parameters.

Statistical summaries for direct and indirect cost parameters will only present results through the first 2 years of treatment. Three-month intervals will be used for analysis of efficacy outcomes and AEs.

For the analysis of efficacy outcomes, a subject is included in the analysis for a 3-month interval if the end date is on or after the *last day* of the 3-month interval and the subject diary was completed for at least 1 day during the 3-month interval.

For the analysis of AEs, a subject is included in the analysis for a 3-month interval if the end date is on or after the *first day* of the 3-month interval.

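### SAP 8.2.1.1 tests 90% diary completion once over each whole seizure-free interval, so a subject can count as seizure-free for 18 months but not for 12

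*SAP*

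**What the plan says.** SAP 8.2.1.1 counts subjects who are "seizure free for all seizure types for any continuous 6-month interval, 12-month interval, 18-month interval, and so forth" while on BRV. Two conditions apply: no seizure is reported in the interval, and "the seizure diary was completed for at least 90% of days within the seizure-free interval".

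For 6 months, the completion percentage is 100 × (180 − days not done)/180. For longer durations, "A similar calculation applies for 12-month seizure freedom based on 360 days, 18-month seizure freedom based on 540 days, and so forth". These denominators rest on SAP 3.2.5: "A month is defined as 30 days".

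The only other failure rule is for short exposure: "Subjects whose duration of BRV treatment was less than the specified duration of seizure freedom will be considered failures for seizure-freedom". The section sets no limit on consecutive not-done days, no threshold for parts of an interval, and no rule that success at one duration implies success at a shorter one. Summaries by exposure duration cohort look only within the cohort interval, so the 18-month cohort is assessed on days 1-540 however long its members were treated.

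SAP 8.2.2.4 carries the derivation over to the PGS subjects. SAP 4.2 plans no summary of the effect of missing diary days.

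The underlying variable in Protocol 4.2.2 names two durations: "Percentage of subjects continuously seizure-free for all seizure types (I+II+III) for at least 6 months and at least 12 months during the Evaluation Period". SAP 8.2.1.1 adds 18 months and leaves the series open.

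**The concern.** A subject who is continuously seizure-free for 18 months is, by plain meaning, also seizure-free for at least 12. A proportional rule applied separately to each duration does not guarantee this, because the longer interval tolerates more not-done days in total and they may all fall together. A 12-month rate, which the protocol names, could then leave out a subject whom the same table counts at 18 months.

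The second issue is what the word continuously can bear. The unbroken stretch without diary data that the rule accepts lengthens with the duration claimed, and the 90% rule is the only protection this variable has against missing diary data.

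**Working it through.** **Inputs.** Month = 30 days (SAP 3.2.5). Threshold 90%, with denominators 180, 360 and 540 days and onward (SAP 8.2.1.1). The interval may lie anywhere on treatment.

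**Tolerated days not done.** For an interval of L days, 100 × (L − n)/L ≥ 90 gives n ≤ 0.1 L.

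| Duration | L (SAP's own figure up to 18 months) | Most days not done |
|---|---|---|
| 6 months | 180 | 18 |
| 12 months | 360 | 36 |
| 18 months | 540 | 54 |
| 24 months, if reported | 720 | 72 |

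The tolerated share stays at 10%; the number of days grows.

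**18 versus 12 months.** Every 360-day window inside days 1-540 contains days 181-360. Put n not-done days there, with no reported seizure. Each 360-day window then has n not-done days, and so does the 540-day interval.

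| n | 12 months: (360 − n)/360 | 18 months: (540 − n)/540 |
|---|---|---|
| 36 | 90.0%, met | 93.3%, met |
| 37 | 89.7%, not met | 93.1%, met |
| 54 | 85.0%, not met | 90.0%, met |
| 55 | 84.7%, not met | 89.8%, not met |

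The inversion therefore needs 37 to 54 not-done days. For example, a gap at days 244-297 (54 days) gives 6 months yes, 12 months no, 18 months yes.

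**24 versus 18 months.** Every 540-day window inside 720 days contains days 181-540. With 55 to 72 not-done days there, 24 months is met (665/720 = 92.4% down to 648/720 = 90.0%) and 18 months is not (485/540 = 89.8% down to 468/540 = 86.7%).

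**Where it cannot happen.** If the longer duration is a whole multiple of the shorter, the long interval splits into whole short ones. When the total is at least 90% complete, at least one piece must be too. So 12 versus 6, 18 versus 6 and 24 versus 12 months never invert.

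**How far it reaches in the overall table.** Take a seizure-free record of T days with one 54-day gap starting on day g. The 12-month result is missed only if the first and the last 360-day windows each hold more than 36 not-done days:

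- First window: 361 − g ≥ 37, so g ≤ 324.
- Last window: g + 53 − (T − 359) + 1 ≥ 37, so g ≥ T − 376.

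Both hold only if T − 376 ≤ 324, that is, T ≤ 700. The share of gap positions is (324 − (T − 376) + 1)/(T − 53):

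| T | Positions giving the 12-month miss | Share |
|---|---|---|
| 540 | 161 of 487 | 33.1% |
| 600 | 101 of 547 | 18.5% |
| 650 | 51 of 597 | 8.5% |
| 700 | 1 of 647 | 0.2% |

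For a 37-day gap at T = 540, the share is 144 of 504 = 28.6%. These shares assume one gap at a random position. They say nothing about how often such gaps occur.

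**Cohort table.** The 18-month cohort is cut at day 540, so the T = 540 row applies to every member with such a gap, whatever the total exposure.

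**The case against.** The strongest reply is that this touches little. It is a descriptive variable outside the secondary efficacy set, no hypothesis is tested, and the two durations that the protocol names cannot contradict each other. In the overall table, a subject with one gap and more than 700 seizure-free days always finds a qualifying 360-day window. All of this stands, and it sets the size of the point. Two things remain. The 18-month cohort table is not rescued by longer exposure. A longer record can also miss 12 months if it holds further gaps, or seizures outside the 540 days.

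Three stronger readings are tempting and are not supported:

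- *The tolerated gap reaches half a year.* That needs a 60-month seizure-freedom result. SAP 5.1 names 60 months only for the Kaplan-Meier retention estimate, and SAP 3.2.7 leaves the last exposure cohort open until database lock. The firm range is 18 to 54 days.
- *From 30 months, one lost diary card still passes.* After Month 3 visits are three months apart ("Next 9 months: 1 visit every 3 months: FEV alternating with MEV") and each card is issued at a visit "and to be returned at the next visit". The tolerance at 30 months is exactly 90 days, so a 91-day gap fails (809/900 = 89.9%); 36 months would then pass (989/1080 = 91.6%). In addition, the card is filled in only on seizure days, and the investigator reviews it with the subject before entering seizures in the CRF. A blank day is therefore not necessarily a not-done day. The documents do not say how a lost card would be flagged.
- *The long-duration rates are materially inflated.* Neither document gives the frequency of gaps or the seizure rate within them, so no size of bias can be derived. The rule that counts short exposure as failure pulls the overall rates down.

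**Conclusion.** The point holds as a minor correction. As written, the rule can produce a self-contradictory result: seizure-free for 18 months and not for 12, given 37 to 54 not-done days within days 181-360 of a 540-day record or of the 18-month cohort interval. The same can occur between adjacent longer durations, such as 24 versus 18 months, if the series is carried that far.

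This rests on the SAP's own formula and on not-done meaning days that the database records as such. It does not depend on any assumed seizure rate. The number of subjects affected is unknown and may be small or zero. The 6-month result is unaffected, and the 12-month rate is affected only by omitting some subjects who are counted at a longer duration.

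**What to change.** In SAP 8.2.1.1, and through it 8.2.2.4, replace the whole-interval test by this rule: the diary must be completed on at least 90% of days (at most 18 not done) in each consecutive 180-day block of the interval, counted from its first day.

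Every reported duration is a multiple of 180 days, so any longer success contains the adjacent passing blocks that make up each shorter one, and nesting is guaranteed. The longest possible blank run is 18 + 18 = 36 days, across a block boundary, at any duration. The 6-month rule does not change. In the 540-day example, gaps of 37 or 54 days then give 6 months yes, 12 and 18 months no.

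**Cost.** One sentence and a small programming change. Rates at 12 months and beyond may fall: a gap of 19 to 36 days within one block now passes 12 months and could then fail.

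**Minimum alternative.** If the sponsor wants to keep the present 12-month threshold, state that a subject who meets a longer duration is counted as meeting all shorter ones. This restores nesting and lowers no rate, but it leaves the tolerated blank run growing with duration.

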8.2.2 Subjects with Primary Generalized Seizures

The following variables are summarized for the Efficacy Population for PGS.

8.2.2.1 All type seizure days

Twenty-eight day adjusted all other type seizure days will be summarized with quantitative descriptive statistics in the same manner as 28-day adjusted POS frequency.

8.2.2.2 Percent reduction in all type seizure days

Percent reduction in all other type seizure days from Baseline will be calculated in the same manner as percent reduction in POS frequency as described in Section 8.1.2. This variable will be summarized in the same manner as percent reduction in POS frequency.

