3.2.4 Study periods

The Baseline Period for N01379 corresponds to the Baseline Period of the previous studies, and is defined for seizure outcomes and direct cost parameters. The Baseline Period is defined as study days on or after the date of Visit 1 and prior to the date of Visit 2 for N01258 and study days on or after the date of Visit 1 and prior to the date of Visit 3 for N01358.

The study is divided into 3 periods: Evaluation Period, Down-Titration Period, and Post-Treatment Period. A subject is classified as “discontinued” if the subject has a termination case report form (CRF) or has an early discontinuation visit (EDV). A subject is classified as “completed” if this subject completes the full extent of the study as defined in the protocol at database lock.

A “discontinued” subject can be potentially slotted into the 3 periods of the study. The following algorithms will be used to slot the subject appropriately into the Evaluation Period, Down-Titration Period, and Post-Treatment Period.

- For Evaluation Period, the start date is the date of first dose of BRV, and the following algorithm is used to determine the end date:
 - If the subject enters the Down-Titration Period, then the date of EDV is the end date;
 - If the subject does not enter the Down-Titration Period but meets 1 of the following criteria, the Evaluation Period ends on date of last dose of BRV:
 - Without an EDV but having a termination CRF,
 - With an EDV and having a termination CRF,
 - With an EDV and the date of EDV prior to the database lock date and having no termination CRF.

- A subject is considered entering Down-Titration Period only if the subject has an EDV and at least 1 dose of study drug after the date of EDV, the start date of Down-Titration Period is set as 1 day after the date of EDV, and the Down-Titration Period ends on date of last dose of BRV. A subject without an EDV but having a termination CRF or with an EDV but without any dosing of study drug after the EDV will not have the Down-Titration Period, and no artificial Down-Titration Period will be created for analysis.
- A subject is considered entering the Post-Treatment Period if the subject has at least 1 contact (scheduled visit, unscheduled visit, or telephone contact) after the date of last dose of BRV. The Post-Treatment Period starts 1 day after date of last dose of BRV irrespective of entering the Down-Titration Period, and there is no end date.

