3.5.2 Efficacy populations

Efficacy Populations will consist of all subjects who took at least 1 dose of study drug and have at least 1 seizure diary day during the Evaluation Period. Separate Efficacy Populations are defined for subjects with focal epilepsy from N01358 and N01258 and subjects with generalized epilepsy from N01258.

A subject will be excluded from the Efficacy Analysis Set for POS or PGS if either they did not receive at least 1 dose of BRV, or the clinical database indicates that the daily seizure diary was not completed for any days on or after the first dose of BRV and on or prior to the end date of the Evaluation Period (see Section 8). Subjects were assigned to a POS population or a PGS population in the previous study, based on diagnosis or medical history.

Seizure outcomes will be summarized for either the Efficacy Population for POS or the Efficacy Population for PGS. Summaries of epilepsy history and QOLIE-31-P will be provided for the Efficacy Populations for both POS and PGS.

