8 EFFICACY ANALYSES

In general, all study outcomes based on seizure frequency will be summarized for the Efficacy Analysis Set for POS and all study outcomes based on seizure days will be summarized for the Efficacy Analysis Set for PGS.

The derivations of 28-day adjusted seizure frequency and 28-day adjusted seizure days are described in detail in Section 3.8.1.2 and Section 3.8.1.3, respectively.

All summaries of efficacy data are descriptive; no statistical testing will be performed.

Because study N01258 was a safety study, subjects were not required to meet seizure frequency requirements during the Baseline Period, and the Baseline Period was short (ie, 7 days). Therefore, subjects from N01258, whether subjects with POS or PGS, will be excluded from efficacy summaries in the variables of percent reduction in POS frequency and responder rates, but subjects from N01258 will be included in the efficacy summary in the variable of the percent of subjects continuously seizure free as this variable is independent from baseline.

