8.1.2 Percent reduction in POS frequency

Percent reduction in POS frequency from Baseline to the On Treatment Period will be calculated as follows, where On Treatment Period Frequency is the 28-day adjusted POS frequency during On Treatment Period and Baseline Period Frequency is the 28-day adjusted POS frequency during the Baseline Period of the previous study.

$$\% \text{ Reduction} = 100 \times \frac{\text{Baseline Period Frequency} - \text{On Treatment Period Frequency}}{\text{Baseline Period Frequency}}$$

A similar calculation applies to each 3-month time interval over the On Treatment Period and for the cohort interval for each exposure duration cohort.

Percent reduction from Baseline for POS frequency will be summarized with quantitative descriptive statistics for the On Treatment Period, and by 3-month time intervals over the On Treatment Period. The summary over the On Treatment Period will include all subjects in the POS Efficacy Analysis Set. Similar summaries will be provided for the full cohort interval

and by 3-month time intervals for each exposure duration cohort. Percent reduction from Baseline for POS frequency will be summarized in the same manner by geographic region.

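### SAP Section 8 rejects the 7-day N01258 baseline, yet 8.2.2.2 and 8.2.2.3 still plan percent reduction and responder outcome for generalized-epilepsy subjects, who have no other baseline

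*SAP*

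**What the plan says.** - **Who is in the PGS set.** SAP 3.5.2 defines the generalized Efficacy Population as "subjects with generalized epilepsy from N01258". No other study contributes.
- **Their baseline.** SAP 3.2.4 sets it as "study days on or after the date of Visit 1 and prior to the date of Visit 2 for N01258". Section 8 describes N01258 as a safety study with a 7-day baseline and no seizure-frequency requirement.
- **The exclusion.** For those reasons Section 8 says that N01258 subjects of either seizure type will be "excluded from efficacy summaries in the variables of percent reduction in POS frequency and responder rates". They stay in the seizure-freedom summary because it does not use baseline.
- **What is still planned.** Protocol 4.2.2 and SAP 2.2.2.2 both list "Percent reduction in generalized (type II) seizure days per 28 days from Baseline of the previous study to the Evaluation Period", together with a responder rate in seizure days. SAP 8.2.2.2 says "Percent reduction in all other type seizure days from Baseline will be calculated in the same manner as percent reduction in POS frequency", and 8.2.2.3 derives a PGS responder outcome on the model of 8.1.3.
- **The formula.** SAP 8.1.2 divides by baseline, where "Baseline Period Frequency is the 28-day adjusted POS frequency during the Baseline Period of the previous study". Neither that section nor any other says what to do when baseline is zero.
- **The protocol's own exception.** Protocol 12.4 drops only responder rates for N01258. It also allows generalized-epilepsy variables to be omitted if there are too few subjects, which is a different reason.

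**The concern.** The sponsor has judged this baseline too short and too unselected to support percent reduction in partial-onset subjects from N01258. The same defect applies to generalized-epilepsy subjects from the same study, but percent reduction in seizure days is missing from the list of excluded variables. A programmer working from 8.2.2.2 would follow its cross-reference to 8.1.2. That section contains no N01258 exclusion and calls for the whole efficacy set, with further summaries by 3-month interval, exposure cohort and region.

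Two things would go wrong in that table. Subjects with no seizure day in the baseline week have no computable value. Subjects with infrequent seizures enter only if they had a seizure day in that week, and then drift back to their usual rate, which looks like improvement. The responder outcome in 8.2.2.3 is a plainer conflict, because Section 8 names responder rates and covers generalized subjects.

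**Working it through.** The documents give no figure for this point, so there is nothing of theirs to reproduce. The check applies the SAP formula to subjects who do not change.

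**Inputs from the documents.** Baseline of 7 days with no seizure requirement (SAP 8). Seizure days scaled to 28 days over completed diary days (SAP 3.8.1.3). Percent reduction = 100 × (baseline − on-treatment)/baseline (SAP 8.1.2).

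**Assumptions.** True rate r seizure days per 28 days (not in the documents, so a range is shown); days independent; all 7 diary days completed; on-treatment rate equal to r.

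**Formulas.** Seizure days in the baseline week: k ~ Binomial(7, r/28). Adjusted baseline = 28k/7 = 4k, so the smallest nonzero baseline is 4 per 28 days. Share undefined = P(k = 0) = (1 − r/28)^7. Apparent reduction for k ≥ 1 is 100 × (1 − r/(4k)).

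**Share undefined.**
- r = 1: (27/28)^7 = 0.775
- r = 2: (26/28)^7 = 0.595
- r = 4: (24/28)^7 = 0.340
- r = 8: (20/28)^7 = 0.095

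**Mean among the rest, worked for r = 4.** P(k = 1, 2, 3, 4, 5) = 0.397, 0.198, 0.055, 0.009, 0.001, with apparent reductions of 0, 50, 66.7, 75 and 80%. The weighted sum is about 14.35; divided by 0.660 it gives 21.7%.

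| True rate per 28 days | Undefined | Mean reduction in the rest | Median | Reduction ≥50% | Increase ≥50% |
|---|---|---|---|---|---|
| 1 | 77.5% | 76% | 75% | 100% | 0% |
| 2 | 59.5% | 55% | 50% | 100% | 0% |
| 4 | 34.0% | 22% | 0% | 40% | 0% |
| 6 | 18.5% | −1% | 25% | 21% | 43% |
| 8 | 9.5% | −15% | 0% | 12% | 29% |
| 12 | 2.0% | −22% | 0% | 3% | 35% |

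The last four columns are among subjects with a nonzero baseline. The mean changes sign near 6 per 28 days.

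**Rates that vary between subjects.** With gamma-distributed rates (shape 1; means 2, 4 and 8 per 28 days), a 90-day on-treatment interval and 400,000 simulated subjects, 66%, 48% and 31% are undefined. The median apparent reduction in the rest is 48%, 28% and 11%. An assumed 56-day baseline would instead give 20%, 11% and 6% undefined and medians of 7%, 3% and 0%. Most of the distortion in the median therefore comes from the short baseline.

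**What is not distorted in this way.** The average of the adjusted baseline itself is E(4k) = 4 × 7 × r/28 = r, because subjects with k = 0 count as zero. The seizure-day summary in 8.2.2.1 therefore does not share the problem.

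**The case against.** The strongest reply is that Section 8 already covers this. Its sentence expressly takes in generalized subjects, and its reason for keeping seizure freedom is that seizure freedom does not depend on baseline. Percent reduction in seizure days does depend on it, and 8.2.2.2 says it is handled like the POS variable from which N01258 is excluded. That reading is fair and may be what was meant. It does not repair the plan: with every PGS subject from N01258, 8.2.2.2 would specify a table with nobody in it.

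Three stronger inferences are tempting, and the documents do not support them.

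- A reader might infer that the plan will certainly report large false reductions. That needs the literal reading and low seizure rates. The rates are not given, the mean bias reverses above about 6 per 28 days, and the median, which the SAP also reports, is 0% at 4 and at 8.
- A reader might infer that this is the only baseline-referenced efficacy result left for generalized epilepsy. It is not: SAP 8.2.3 plans change from baseline in QOLIE-31-P for the PGS set, and 8.2.2.1, through 8.1.1, tabulates seizure days at baseline and on treatment.
- A reader might infer that adjusted baselines can only be multiples of 4. That holds only when all 7 diary days were completed, since SAP 3.8.1.3 divides by completed days.

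**Conclusion.** The inconsistency is firm and rests on the text alone. Section 8 and 8.2.2.3 contradict each other on the PGS responder outcome. Section 8 and 8.2.2.2 leave percent reduction in seizure days either empty or computed from a baseline the SAP has itself rejected, with no rule for division by zero.

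The numerical size is conditional. Under the stated assumptions, and at rates of 1 to 8 seizure days per 28, between 78% and 9.5% of values are undefined. The mean apparent change in the rest runs from a 76% reduction to a 15% increase with no drug effect.

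The consequence is limited. Both outcomes are non-secondary efficacy variables, all summaries are descriptive with no testing, and at most 100 subjects come from N01258 (Protocol 5.1.2), of whom only those with generalized epilepsy are concerned. No primary or secondary variable changes. It should be corrected because the sponsor has already accepted the reason and the correction is nearly free.

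**What to change.** 1. In SAP Section 8, add percent reduction in seizure days to the variables from which N01258 subjects are excluded.
2. Mark 8.2.2.2 and 8.2.2.3 as not performed.
3. In SAP 2.2.2.2, note that these two Protocol 4.2.2 variables are not assessed because of the short N01258 baseline.
4. Keep what is already planned: 28-day adjusted seizure days by interval (8.2.2.1) and seizure freedom (8.2.2.4).
5. While editing, align the variable name. SAP 2.2.2.2 refers to generalized type II seizure days, the headings of 8.2.2.1 to 8.2.2.3 to all types, and their text to all other types.

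If the sponsor prefers to keep 8.2.2.2, it needs an explicit exception to the Section 8 reasoning, a zero-baseline rule, the count of undefined values beside each summary, and a caution on interpretation.

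The cost is a few lines of SAP wording and the removal of two small sets of tables. No data collection changes.
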